#### **10.4.4.3 Pregnancy testing**

Pregnancy testing will consist of serum testing at the Screening. The pregnancy test will be urine at all other visits.

A by-subject listing of the pregnancy test data will be provided by treatment group.

#### **10.4.4.4 Childbearing potential and Lifestyle**

Childbearing potential and lifestyle will be collected at Screening. A by-subject listing will be provided for all the subjects screened.

#### **10.4.4.5 Patient Health Questionnaire 9 (PHQ-9)**

The PHQ-9 is a multipurpose instrument for screening, diagnosing, monitoring, and measuring the severity of depression. The PHQ-9 scores for depression range from 0 to 27 with higher scores indicating worse state. A score of 5-9 is considered to be minimal symptoms of depression. A score of 10 to 14 is considered minor depression, dysthymia, or mild major depression. A score of 15 to 19 is considered to indicate moderately severe major depression, and a score  $\geq 20$  is considered to be severe major depression. If any of the 9 questions are missing, then the score is treated as missing.

Change from Baseline in PHQ-9 is derived as post-Baseline score minus Baseline score and will be summarized by treatment group.

Differently to other safety variables, PHQ-9 will be summarized using the MCMC/monotone regression approach described in Section 8.1.3.1. A table for the SS through Week 48 will be produced. An additional table will be produced for the OLS by treatment sequence and visit.

---

The number and percentage of subjects with a PHQ-9 score  $\geq 15$  at any point while on treatment and the number and percentage of subjects with a PHQ-9 score  $\geq 20$  at any point while on treatment will also be presented based on observed case data.

A by-subject listing of PHQ-9 data will be provided separately for the OLE and the OLE2 treatment periods. This listing will include site, subject number, visit, total score observed result, and total score change from Baseline value.

PUBLIC COPY  
This document cannot be used to support any marketing authorization application and any extensions or variations thereof.

---

## 12 APPENDICES

### 12.1 Appendix A: MedDRA algorithmic approach to anaphylaxis

The SMQ *Anaphylactic reaction* consists of three parts:

1. A **narrow search** containing PTs that represent core anaphylactic reaction terms
  - Category A – core anaphylactic reaction terms
    - Anaphylactic reaction
    - Anaphylactic shock
    - Anaphylactic transfusion reaction
    - Anaphylactoid reaction
    - Anaphylactoid shock
    - Circulatory collapse
    - Dialysis membrane reaction
    - Kounis syndrome
    - Procedural shock
    - Shock
    - Shock symptom
    - Type I hypersensitivity
  - 2. A **broad search** that contains additional terms that are added to those included in the narrow search. These additional terms are signs and symptoms possibly indicative of anaphylactic reaction and categorized in B, C, or D.
    - Category B (Upper Airway/Respiratory terms)
      - Acute respiratory failure
      - Asthma
      - Bronchial oedema
      - Bronchospasm
      - Cardio-respiratory distress
      - Chest discomfort
      - Choking
      - Choking sensation
      - Circumoral oedema
      - Cough
      - Cough variant asthma

- 
- Cyanosis
  - Dyspnoea
  - Hyperventilation
  - Irregular breathing
  - Laryngeal dyspnoea
  - Laryngeal oedema
  - Laryngospasm
  - Laryngotracheal oedema
  - Mouth swelling
  - Nasal obstruction
  - Oedema mouth
  - Oropharyngeal oedema
  - Oropharyngeal spasm
  - Oropharyngeal swelling
  - Pharyngeal oedema
  - Pharyngeal swelling
  - Respiratory arrest
  - Respiratory distress
  - Respiratory failure
  - Reversible airways obstruction
  - Sensation of foreign body
  - Sneezing
  - Stridor
  - Swollen tongue
  - Tachypnoea
  - Throat tightness
  - Tongue oedema
  - Tracheal obstruction
  - Tracheal oedema
  - Upper airway obstruction
  - Wheezing

- Category C (Angioedema/Urticaria/Pruritus/Flush terms)
  - Acquired C1 inhibitor deficiency
  - Allergic oedema
  - Angioedema
  - Circumoral swelling
  - Erythema
  - Eye oedema
  - Eye pruritus
  - Eye swelling
  - Eyelid oedema
  - Face oedema
  - Flushing
  - Hereditary angioedema with C1 esterase inhibitor deficiency
  - Injection site urticaria
  - Lip oedema
  - Lip swelling
  - Nodular rash
  - Ocular hyperaemia
  - Oedema
  - Oedema blister
  - Periorbital oedema
  - Periorbital swelling
  - Pruritus
  - Pruritus allergic
  - Rash
  - Rash erythematous
  - Rash pruritic
  - Skin swelling
  - Swelling
  - Swelling face
  - Swelling of eyelid

- 
- Urticaria
  - Urticaria papular
  - Category D (Cardiovascular/Hypotension terms)
    - Blood pressure decreased
    - Blood pressure diastolic decreased
    - Blood pressure systolic decreased
    - Cardiac arrest
    - Cardio-respiratory arrest
    - Cardiovascular insufficiency
    - Diastolic hypotension
    - Hypotension
    - Hypotensive crisis
    - Post procedural hypotension
3. An **algorithmic approach** which combines a number of anaphylactic reaction symptoms in order to increase specificity. A case must include one of the following where both occur on either the same day as when an injection was administered or one day after, and for scenarios where two must have been reported, both events must have occurred within one day of each other:
- A narrow term or a term from Category A
  - A term from Category B – (Upper Airway/Respiratory) AND a term from Category C – (Angioedema/Urticaria/Pruritus/Flush)
  - A term from Category D – (Cardiovascular/Hypotension) AND [a term from Category B – (Upper Airway/Respiratory) OR a term from Category C – (Angioedema/Urticaria/Pruritus/Flush)]
  - Hypersensitivity events will be identified using the “Hypersensitivity (SMQ)”. All TEAEs which code to a PT included in the Scope=Narrow search will be included.

## 12.2 Appendix B: Definition of CTCAE grades

**Table 12–1: Definitions of CTCAE grades by biochemistry parameter**

Parameter (unit)	Definition	Unit	Grade 1	Grade 2	Grade 3	Grade 4
Alanine Aminotransferase	High	UL	>ULN - 3.0 x ULN	>3.0 - 5.0 x ULN	>5.0 - 20.0 x ULN	>20.0 x ULN
Alkaline Phosphatase	High	UL	>ULN - 2.5 x ULN	>2.5 - 5.0 x ULN	>5.0 - 20.0 x ULN	>20.0 x ULN
Aspartate Aminotransferase	High	U/L	>ULN - 3.0 x ULN	>3.0 - 5.0 x ULN	>5.0 - 20.0 x ULN	>20.0 x ULN
Bilirubin	High	umol/L	>ULN - 1.5 x ULN	>1.5 - 3.0 x ULN	>3.0 - 10.0 x ULN	>10.0 x ULN
Gamma Glutamyl Transferase	High	U/L	>ULN - 2.5 x ULN	>2.5 - 5.0 x ULN	>5.0 - 20.0 x ULN	>20.0 x ULN
Glucose	High	mg/dL	Fasting glucose value >ULN - 160 mg/dL;	Fasting glucose value >160 - 250 mg/dL;	>250 - 500 mg/dL hospitalization indicated	>500 mg/dL lifethreatening consequences
Creatinine	High	mmol/L	>ULN- 1.5 x ULN	(>1.5 – 3.0) x ULN	(>3.0 – 6.0) x ULN	6.0 x ULN
Sodium	Low	mmol/L	130- <LLN	N/A	120-<130	<120
Sodium	High	mmol/L	>ULN- 150	>150- 155	>155-160	>160
Potassium	Low	mmol/L	3.0- <LLN	3.0- <LLN	2.5-<3.0	<2.5
Potassium	High	mmol/L	>ULN- 5.5	>5.5- 6.0	>6.0-7.0	>7.0
Calcium	Low	mmol/L	2.0- <LLN	1.75- <2.0	1.5-<1.75	<1.5
Calcium	High	mmol/L	>ULN- 2.9	>2.9- 3.1	>3.1-3.4	>3.4

Magnesium	Low	mmol/L	0.5- <LLN	0.4- <0.5	0.3-<0.4	<0.3
Magnesium	High	mmol/L	>ULN- 1.23	N/A	>1.23-3.30	>3.30
Total cholesterol	High	mmol/L	>ULN- 7.75	>7.75- 10.34	>10.34-12.92	>12.92
Triglyceride	High	mmol/L	1.71 - 3.42	>3.42 - 5.7	>5.7 - 11.4	>11.4

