### 10.3 Clinical laboratory evaluations

If not specified otherwise, laboratory values, including markedly abnormal laboratory values will be presented descriptively by treatment group for the SS. Tables presenting markedly abnormal values and those based on CTCAE grade only include selected laboratory variables.

For tables where data are summarized by visit, unscheduled and repeat visits will not be summarized, but these data will be included in listings. For tables where multiple measurements over a period of time are considered (as in shift tables), unscheduled and repeat visits will be considered as long as they were collected in the period being summarized. All summaries will be presented in SI units and will be based on observed case values. In the case where laboratory values are below the lower limit of quantification, then these will be set to the midpoint between 0 and the lower limit of quantification for the purpose of summarizing the data. The following summaries are required:

- A summary of observed results and change from Baseline values in each laboratory variable by treatment group and visit
- A summary of the number and percentage of subjects experiencing markedly abnormal values at any time while on treatment (assessment on or following the first dose of study treatment through the final dose of study treatment + 140 days) by laboratory variable and treatment group. Two separate tables will show results for the initial treatment period (for the SS) and the Initial and Maintenance Treatment Period (for the MS). An additional table for the OLE period will be provided for the OLS by treatment the subjects were receiving at the time of the assessment of the abnormal value.
- A summary of the number and percentage of subjects with a given CTCAE grade (0, 1, 2, 3, or 4) based on minimum/maximum post-baseline value by laboratory variable and treatment group. Two separate tables will show results for the initial treatment period (for the SS) and the Initial and Maintenance Treatment Period (for the MS). An additional table for the OLE period will be provided for the OLS by treatment the subjects were receiving at the time of the assessment of the value with the given CTCAE grade.

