Markedly abnormal values are defined as those with a severity of Grade 3 and above based on the common terminology criteria for adverse events (CTCAE) criteria (U.S. Department of Health and Human Services 2010). Definitions of markedly abnormal values using the Grade 3 cut points are given in the tables below for age ranges of  $\geq 17$  years (Table 10–1 for markedly abnormal liver function test values, Table 10–2 for markedly abnormal biochemistry values and Table 10–3 for markedly abnormal hematology values). Tables summarizing markedly abnormal values should include a summary (counts and percentages) of markedly abnormal labs observed at any time while on treatment (ie, treatment-emergent markedly abnormal [TEMA]). For this summary, Baseline values and values observed more than 140 days after the last administration of study medication are not considered. The laboratory results classified as Grade 3 or Grade 4 will be summarized and listed separately.

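### Table 10-2 gives two different cuts for markedly low glucose: 40 mg/dL is 2.2 mmol/L, not the printed 1.7 mmol/L, and Table 12-1 has no low-glucose row to settle it

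*SAP*

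**What the plan says.** Four statements in the SAP bear on this.

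- **Meaning of the cuts.** Section 10.3 states: "Markedly abnormal values are defined as those with a severity of Grade 3 and above". It adds: "Definitions of markedly abnormal values using the Grade 3 cut points are given in the tables below". The cuts in Table 10-2 are therefore meant to be the points at which CTCAE Grade 3 begins.
- **The glucose cuts.** Table 10-2 has a conventional-unit column and a standard-unit (SI) column. For glucose, the low cut is <40 mg/dL in the first and <1.7 mmol/L in the second. The high cut is >250 mg/dL and >13.9 mmol/L.
- **Units of reporting.** For laboratory data, Section 10.3 says: "All summaries will be presented in SI units and will be based on observed case values".
- **Grading.** Section 10.3 plans tables of "subjects with a given CTCAE grade (0, 1, 2, 3, or 4) based on minimum/maximum post-baseline value", shift tables on the same basis, and a further split: "The laboratory results classified as Grade 3 or Grade 4 will be summarized and listed separately". The grades are defined in Appendix B, Table 12-1. Its single glucose row is labelled High and given in mg/dL; the Grade 1 cell opens with "Fasting glucose value >ULN - 160 mg/dL". Sodium, potassium, calcium and magnesium each have both a Low and a High row.

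**The concern.** The two columns of Table 10-2 should express one threshold in two units. For low glucose they express two thresholds, so the count of markedly low values depends on which column is applied. Because reporting is in SI units, the natural reading of the plan applies the stricter figure, 1.7 mmol/L. A subject can then meet the SAP's mg/dL criterion and still be left out of the markedly abnormal tables for the Initial Treatment Period, the Initial and Maintenance Treatment Period, and the OLE.

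The grade definitions would normally resolve such a conflict, but Table 12-1 has no entry for low glucose. The same gap means the instruction to report Grade 3 and Grade 4 separately cannot be carried out for low glucose from the SAP's own tables: Table 10-2 gives a point of entry to Grade 3, and nothing in the SAP says where Grade 4 begins.

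**Working it through.** **1. Conversion factor from the SAP's own row.** High glucose is 250 mg/dL and 13.9 mmol/L:

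250 / 13.9 = 17.99 mg/dL per mmol/L.

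**2. Apply it to the low cut.**

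- 40 / 17.99 = 2.22 mmol/L, against the printed 1.7.
- 1.7 × 17.99 = 30.6 mg/dL, against the printed 40.
- 1.7 / 2.22 = 0.766, so the printed SI cut is about 23% below the converted one.

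**3. Could rounding explain it?** The 13.9 could stand for anything from 13.85 to 13.95, giving factors of 250/13.95 = 17.92 to 250/13.85 = 18.05. Then 40 mg/dL lies between 40/18.05 = 2.216 and 40/17.92 = 2.232 mmol/L. If 1.7 is a rounded 1.75 at most, it is at most 1.75 × 18.05 = 31.6 mg/dL. Rounding cannot bring the two cuts together. The molar mass of glucose (180.156 g/mol, a physical constant that is not in the SAP) gives the same answer: 40 × 10 / 180.156 = 2.22.

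**4. Is the rest of the table consistent?** The other mg/dL–mmol/L pairs, converted as mg/dL × 10 / molar mass:

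| Cut in Table 10-2 | Converted (mmol/L) | Printed (mmol/L) | Printed / converted |
|---|---|---|---|
| Glucose >250 | 13.877 | 13.9 | 1.002 |
| Calcium >12.5 | 3.119 | 3.1 | 0.994 |
| Calcium <7.0 | 1.747 | 1.75 | 1.002 |
| Magnesium >3.0 | 1.234 | 1.23 | 0.997 |
| Magnesium <0.9 | 0.370 | 0.4 | 1.08 |
| Total cholesterol >400 | 10.345 | 10.34 | 0.999 |
| HDL <40 | 1.035 | 1.04 | 1.005 |
| LDL ≥190 | 4.914 | 4.90 | 0.997 |
| Triglycerides >500 | 5.647 | 5.7 | 1.009 |
| **Glucose <40** | **2.220** | **1.7** | **0.766** |

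All agree within 1% except low magnesium, which is 0.370 shown to one decimal, and low glucose, which no rounding reproduces.

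**5. Is it an artefact of reading the table?** No. The amendment log (Section 13.3, Change #35) reprints the table with <40 and <1.7 together on their own line, marked abnormal low.

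**6. The affected band.** The columns disagree for values from 1.7 to <2.2 mmol/L, that is, 30.6 to <40 mg/dL.

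**7. What share of values below 40 mg/dL falls in that band?** With F the distribution of glucose values, the share is [F(2.22) − F(1.7)] / F(2.22). The SAP gives no distribution, so every F here is an assumption:

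- flat from zero: 23%
- density rising linearly from zero: 41%
- normal, mean 5.0 to 6.0 mmol/L: 82% to over 99% for SD 0.6 to 1.0; 56% to 65% for SD 1.5; 40% to 46% for SD 2.0
- lognormal, median 5.0 to 5.5, log-SD 0.15 to 0.40: 84% to over 99%

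The share thus runs from about a quarter to nearly all.

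**The case against.** The arithmetic is not open to dispute, but its reach is limited, and several stronger readings fail.

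- **That most markedly low values are missed.** A reader might infer this because the band is the upper part of the range below 40 mg/dL. The SAP supplies no glucose distribution, and the share is under half in several of the cases tried.
- **That a safety decision threshold is wrong.** Section 10.3 uses these cuts to count and list values. The SAP attaches no stopping or monitoring rule to them, and glucose is not among the safety topics in Section 10.2.3. This is a reporting threshold.
- **That the values disappear.** They enter the observed and change-from-Baseline summaries at scheduled visits, where Section 3.1 has the minimum reported, and the by-subject listings, where abnormal results are flagged. Values from unscheduled or repeat visits are left out of the by-visit summaries, so in the disputed band those rest on the listings alone.
- **That the missing low row in Table 12-1 is plainly a mistake.** Section 10.3 says: "Tables presenting markedly abnormal values and those based on CTCAE grade only include selected laboratory variables". HDL and LDL also have cuts in Table 10-2 and no row in Table 12-1, so the omission may be deliberate. It still sits badly with calling the low-glucose cut a Grade 3 cut and with reporting Grades 3 and 4 separately. One might also infer that a low value would be shown as Grade 0, but the SAP does not define Grade 0 or say how an ungraded direction is displayed.
- **That the 1.7 is known to be the faulty figure, or is known to be programmed.** No program is in the document, and Table 12-1 itself uses mg/dL for glucose. The SAP shows that the columns disagree, not which one departs from the cited criteria.

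What stands after all this is the mismatch and the absence of anything in the SAP to resolve it.

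**Conclusion.** The point holds as a wrong stated threshold. The two low-glucose cuts in Table 10-2 differ by a factor of 0.766. With summaries in SI units, the plan as written leaves values from 1.7 to <2.2 mmol/L out of the markedly abnormal counts although they meet its mg/dL criterion. This rests on the row's own conversion and on the SI column being applied, as Section 10.3 implies.

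The number of subjects cannot be derived from the SAP and is probably small. No primary or secondary efficacy variable is touched. The gap in Table 12-1 is a secondary inconsistency: possibly a choice, but one the SAP does not state. The correction is worth making because a prespecified safety count should not depend on which column is read.

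**What to change.** 1. Reconcile the two low-glucose entries in Table 10-2 against the CTCAE version cited in the SAP (4.0). If <40 mg/dL is the intended Grade 3 cut, the SI entry becomes <2.2 mmol/L. If 1.7 mmol/L is intended, the mg/dL entry has to change to about 31.
2. Reconcile Table 12-1 with the result. Either add a low-glucose row in mmol/L, with bands taken from the cited CTCAE version (the SAP does not print them) and a Grade 3 boundary that matches Table 10-2, or state that low glucose is not graded and how it is treated when Grades 3 and 4 are reported separately.
3. Give the existing high-glucose row in mmol/L too. By the same factor, 160, 250 and 500 mg/dL are 160/17.99 = 8.9, 13.9 and 500/17.99 = 27.8 mmol/L.

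The cost is edits to two tables, one threshold in the programs and, if a low row is added, minor reprogramming of the grade and shift tables for the periods concerned. If the SI cut rises, slightly more low-glucose values may be reported.

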- A shift table of the number and percentage of subjects experiencing CTCAE grade 0, 1, 2, 3, or 4 values (as applicable) at Baseline to minimum/maximum post-Baseline CTCAE grade, by laboratory variable and treatment group. Two separate tables will show results for the initial treatment period (for the SS) and the Initial and Maintenance Treatment Period (for the MS). An additional table for the OLE period will be provided for the OLS by treatment the subjects were receiving at the time of the assessment of the value with the given CTCAE grade. A lipid profile table of treatment emergent markedly abnormal laboratory data will be provided for the Initial and Maintenance Treatment Period (SS) and the Open-label Extension treatment period (OLS) separately.

In addition, a shift table of number and percentage of subjects experiencing post-Baseline HDL Low risk ( $\geq 1.55$  mmol/L), Intermediate risk ( $\geq 1.04 - < 1.55$  mmol/L) and High risk ( $< 1.04$  mmol/L) compared to baseline will be provided for the Initial and Maintenance Treatment Period (SS) and the Open-Label Extension Treatment Period (OLS).

Shift laboratory summaries will use the Baseline for Open-Label Extension Period for subjects switching from secukinumab to Bimekizumab as described in Section 3.2.

A figure of neutrophil values over time for subjects with at least one markedly abnormal neutrophil value (CTCAE Grade 3 or 4) will also be presented.

A by-subject listing of all laboratory data (including urinalysis) will be provided. Separate by-subject listings for the OLE and the OLE2 treatment periods will be provided. These listings will be presented by treatment group and will include: center, subject identifier, age, sex, race, weight, visit, laboratory variable, result (with abnormal values flagged as “L” or “H” accordingly) and unit.

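### Table 12-1 gives Grade 1 and Grade 2 low potassium the same range, so the planned CTCAE grade and shift tables cannot separate these two grades

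*SAP*

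**What the plan says.** Section 10.3 (Clinical laboratory evaluations) plans two kinds of output that need a CTCAE grade for each value.

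- The grade table counts "subjects with a given CTCAE grade (0, 1, 2, 3, or 4) based on minimum/maximum post-baseline value", separately for each parameter and arm.
- The shift table compares grades "at Baseline to minimum/maximum post-Baseline CTCAE grade, by laboratory variable and treatment group".

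Each is planned for the Initial Treatment Period, for the Initial and Maintenance Treatment Period, and for the OLE Period. Appendix C (Section 12.3) also lists CTCAE laboratory data among the Week 96 outputs.

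The grades are defined in Appendix B. For low potassium, Table 12-1 reads "3.0- <LLN 3.0- <LLN 2.5-<3.0" for Grades 1, 2 and 3, with Grade 4 below 2.5 mmol/L. No footnote or clinical qualifier accompanies the row. Two other rows of the same table are useful for comparison: low calcium, "2.0- <LLN 1.75- <2.0 1.5-<1.75", and low sodium, "130- <LLN N/A 120-<130".

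Section 10.3 sets two limits on how far this reaches. The tables of markedly abnormal values and "those based on CTCAE grade only include selected laboratory variables", and the selection is not listed there. In addition, "Markedly abnormal values are defined as those with a severity of Grade 3 and above".

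**The concern.** A grade count or a shift cell needs exactly one grade per value. Two identical ranges cannot supply one for low potassium, so the split between Grade 1 and Grade 2 falls to whoever writes the program. Two programmers could both follow the SAP and deliver different tables, and an independent check of the programming could not say which is right.

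The same gap exists at Baseline. If the Baseline and post-Baseline sides happened to be coded differently, a subject whose potassium did not change could appear to shift between grades.

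**Working it through.** No power, alpha or sample-size figure is involved. The check is to apply the grading row literally.

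**Inputs**
- From Table 12-1, low potassium in mmol/L: Grade 1 = [3.0, LLN); Grade 2 = [3.0, LLN); Grade 3 = [2.5, 3.0); Grade 4 = below 2.5. Lower bounds are included and upper bounds excluded, as the table writes them.
- The potassium LLN is not in the SAP. For illustration it is assumed to be 3.3, 3.5 or 3.6.

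**Step 1: grades per value, on a 0.1 mmol/L grid**

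| Assumed LLN | Values with two grades | Count |
|---|---|---|
| 3.3 | 3.0 to 3.2 | 3 |
| 3.5 | 3.0 to 3.4 | 5 |
| 3.6 | 3.0 to 3.5 | 6 |

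In each case every value in [3.0, LLN) receives Grades 1 and 2 together. Every value below 3.0 receives Grade 3 or Grade 4 only, and every value at or above LLN receives Grade 0 only for the low direction. The overlap is complete for any LLN above 3.0, so the finding does not depend on which LLN is assumed.

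**Step 2: the other low-direction rows**

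The same classification was run on sodium, calcium, magnesium, hemoglobin, platelets, WBC, lymphocytes and neutrophils. None had a value with two grades. Low calcium shows the usual pattern, in which Grade 2 starts where Grade 1 stops (2.0). Low sodium has no Grade 2 range and the table says so.

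**Step 3: effect on the tables**

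Let p be the proportion of subjects whose lowest post-baseline potassium lies in [3.0, LLN).
- Higher grade taken: Grade 1 = 0, Grade 2 = p.
- First match taken: Grade 1 = p, Grade 2 = 0.
- Under either rule, Grade 1 + Grade 2 = p.

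A subject in the interval at Baseline and again post-Baseline falls in the Grade 2 to Grade 2 cell under the first rule and in the Grade 1 to Grade 1 cell under the second. The SAP gives no value for p and no basis for estimating it.

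**Step 4: is there a tie-break?**

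The minimum/maximum wording in Section 10.3 selects among a subject's assessments. It does not say which grade a single value receives, and it is silent on the Baseline grade.

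**Step 5: is this an extraction fault?**

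The copy of the table in the log for Amendment 4 (Section 13.4) shows the same row, so a slip in reading one page is unlikely. The finding rests on Table 12-1 itself.

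**The case against.** The strongest reply is that very little turns on this. The tables are descriptive, and no test uses them. Any single programming rule would treat all arms alike, so it introduces no bias between treatments. Observed values and changes are summarized by visit and all laboratory data are listed, so the combined count in the interval can be recovered. Both candidate labels lie below the SAP's own threshold for a markedly abnormal value. All of this stands, and it fixes the weight of the point as minor. It does not supply the missing rule.

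A second reply is that potassium may not be among the selected variables, and that Section 10.3 tempers the shift-table grades with a phrase about applicability. Inclusion is likely, since potassium has its own rows in Table 12-1, but it is not stated. The applicability phrase leaves some room but assigns no grade, and the grade summary carries no such phrase.

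A third reply is that the source criteria may separate the two grades by a clinical qualifier. The glucose row of Table 12-1 does carry clinical wording, so this is possible. The potassium row carries none, however, and the planned tables are built from laboratory values.

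Two stronger readings are tempting, and the SAP supports neither.
- A reader might infer that the grade and shift tables as a whole are undetermined. Only one split, for one parameter in one direction, is affected.
- A reader might infer from the sodium row that Grade 2 should be marked not applicable for potassium too. The sodium row shows only that sodium has no Grade 2 range. Copying it would label every such value Grade 1, and the SAP gives no ground for that choice.

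**Conclusion.** The point holds in a narrow form. Table 12-1 gives Grade 1 and Grade 2 low potassium the same range, Section 10.3 grades on the laboratory value, and no rule chooses between the two. All values from 3.0 mmol/L to below LLN are ambiguous between these grades, at Baseline and post-Baseline, in every period for which the tables are planned. The reported Grade 2 count is therefore either the whole of that group or none of it.

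This assumes that potassium is among the variables selected for the CTCAE tables and that its LLN is above 3.0. Grades 0, 3 and 4 are uniquely assigned. The markedly abnormal tables use Grade 3 and above (potassium below 3.0 in Table 10-2) and do not change. Nor do the other low-direction rows checked, or any efficacy result. The correction is worth making because it is cheap, not because a conclusion is at risk.

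**What to change.** In the low-potassium row of Table 12-1, replace the two identical cells with one combined category, Grade 1/2: 3.0 to below LLN. Use that category on both the Baseline and post-Baseline sides of the grade and shift tables, for the initial, initial plus maintenance and OLE periods. State it in Section 10.3 or in a footnote to Table 12-1, because Section 10.3 currently lists Grades 1 and 2 separately. A combined category is the neutral option: it claims no separation that the laboratory value cannot support.

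The cost is one table row plus matching labels in the affected tables. No data collection or other analysis changes.
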